### **Analysis Populations**

The intent-to-treat population, consisting of all subjects who signed the informed consent form and were randomized, will be used as the primary population for efficacy analyses. The safety analysis population will include all subjects who signed informed consent and received any amount of study drug. The trial results will be reported according to guidelines specified in the Revised Consolidated Standards of Reporting Trials (CONSORT) statement. A flow diagram describing screening, recruitment, randomization, dropout, and vital status will be included in the primary study report.

### **Statistical Analyses**

## **Demographic and Baseline Data**

Descriptive statistics will be used to summarize demographic, baseline subject characteristics and to assess safety. Continuous-scaled variables (e.g., age) will be summarized with means, medians, standard deviations, quartiles, and minimum and maximum values. Categorical variables (e.g., sex) will be summarized using patient counts and percentages. Baseline medical histories, medications and pre-existing conditions will be summarized by treatment groups.

## **Efficacy Analyses**

### **Primary Efficacy Outcome Variable and Analysis**

The primary efficacy analysis will estimate the mean rank change in %FVC from Baseline to Week 52. Data will be analyzed using a rank linear regression model with the rank change in %FVC from Baseline to Week 52 as the outcome variable and rank Baseline %FVC and HP therapy (placebo or pirfenidone) and concomitant immunosuppressive therapy as covariates. The treatment effect will be tested using the Wald test.

The primary efficacy analysis will be tested at an alpha level of 0.05. Missing data due to reasons other than death will be replaced with imputed values using the MICE method (multiple imputation via chained equations). Missing data due to lung transplant will be imputed using the MICE method even if the subject dies after lung transplant.

Subjects with missing assessments due to death will be ranked worse than those who remain alive. Subjects who die will be ranked according to the time until death, with the shortest time until death as the worst rank.

Supportive analyses of the primary efficacy outcome will include the following:

1. Landmark analyses of mean change in %FVC from Baseline to Weeks 13, 26, 39 and 52.
2. Mean rank change in %FVC compared to Baseline across all study time points using a rank linear mixed effects model for repeated measures.

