### *Disease-Related Exclusions*

1. Not a suitable candidate for enrollment or unlikely to comply with the requirements of this study, in the opinion of the investigator
2. Cigarette smoking at Screening or unwilling to avoid tobacco products throughout the study
3. Known explanation for the interstitial lung disease, including but not limited to radiation, drug toxicity, sarcoidosis, pneumoconiosis.
4. Clinical diagnosis of any connective tissue disease, including but not limited to scleroderma, polymyositis/dermatomyositis, and rheumatoid arthritis.
5. Expected to receive a lung transplant within 6 to 12 months from randomization or on a lung transplant waiting list at randomization.
6. The investigator judges that there has been sustained improvement in the severity of FHP during the 6-12 months prior to Screening Visit 1, based on changes in %FVC, %DLCO, and/or HRCT scans of the chest.

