### *Key Secondary Efficacy Outcome Variables*

1. Progression-free survival (PFS) defined as the time from study treatment randomization to the first occurrence of any of the following events:
  - a. Relative decline from baseline in  $\geq 10\%$  in FVC and/or DLCO
  - b. Acute exacerbation of FHP defined as acute respiratory declined leading to hospitalization or ER or Urgent care evaluation; or evidence of all of the following criteria within a 4-week period in the outpatient setting:
    - i. Increase from baseline  $\text{FIO}_2 \geq 1 \text{ L O}_2$ .
    - ii. Clinically significant worsening of dyspnea and/or cough.
    - iii. New, superimposed ground-glass opacities or consolidation or new alveolar opacities on chest x-ray or CT.
    - iv. Primary: if all other causes excluded (e.g., acute gastro-esophageal aspiration, pneumothorax, infection, left heart failure, pulmonary

embolism, or identifiable cause of acute lung injury).

- c. A decrease from baseline of at least 50 meters in 6-minute walk distance.
- d. Change in background therapy (need for a new course of PO or IV steroids or for the patient receiving maintenance prednisone, as a need to increase the dose by 10 mg or more; and/or addition of cyclophosphamide, azathioprine, mycophenolate mofetil or mycophenolic acid).
- e. Death

2. Slope of FVC over 52-week treatment period.
3. Mean change in %DLCO at week 52
4. Proportion of patients with all-cause mortality.
5. Proportion of patients with all-cause hospitalization.
6. Proportion of patients with hospitalization for respiratory cause.
7. Proportion of patients with respiratory exacerbations requiring hospitalizations.
8. Proportion of patients with evidence of progression in fibrosis on visual comparison of baseline and week 52 HRCT scans.

*Exploratory Outcome Variables:*

1. Mean change from baseline in health-related quality of life, measured by St. George's Respiratory Questionnaire (SGRQ) (3 domain scores and total score), at Week 52.
2. Mean change from baseline in health-related quality of life, measured by A Tool to Assess Quality of Life Questionnaire (L-IPF) at Week 52.
3. Mean change from Baseline to Week 52 in dyspnea as measured by the University of California at San Diego Shortness-of-Breath Questionnaire (UCSD SOBQ) score.
4. Proportion of patients with evidence of progression, stability or improvement in fibrosis on texture-based quantitative analysis of CT.

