## **STUDY ASSESSMENTS**

Patients will be screened for study inclusion over a period of up to 4 weeks. If eligible, subjects will receive study drug starting on Day 1 (clinic visit). Subjects will have a telephone assessment at Week 1 and 3 and in-clinic assessments on week 5, 13, 26, 39, and 52. Study assessments will include laboratory tests, spirometry, DLCO, 6MWT and Borg Scale, ECG, HRCT scan, patient reported outcome questionnaires, vital signs, height, weight, oxygen saturation and fraction of inspired oxygen (FiO2), directed history, physical examination and any changes to existing treatment regimens. Subjects will complete an AE and dosing compliance diary between all visits. Subjects who undergo lung transplantation or who chose to withdraw from study procedures early will be followed for vital status until Week 52.

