### **Vital Status Assessments**

Vital status will be assessed for those who are no longer able to participate in the study procedures (Early Withdrawal from Study Procedures) at protocol-specified time points (study visit dates) until the Follow-Up Visit. Subjects who undergo lung transplantation or who chose to withdraw from study procedures early will be followed for vital status until Week 52. This assessment will most likely be accomplished remotely (i.e., via telephone or electronically). These communications are well documented in the participants study file. Vital status procedures are as follows:

1. If the subject is not available, an authorized family member or representative will be contacted by telephone or electronically at the milestones of study visit dates.
2. In the case of lung transplant, the date of the transplant, details of the transplant, dates of hospitalization, and the current vital status will be obtained.
3. In the case of a subject death, the date, details, and cause of death will be requested from the subject's representative or family member.
4. If a subject is lost to follow-up, vital status will be ascertained through the use of death registries.

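### Does the primary analysis contradict itself by imputing a value for a subject who dies after lung transplant?

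*Combined protocol and SAP*

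**What the plan says.** The rules are in the section Primary Efficacy Outcome Variable and Analysis, in two consecutive paragraphs.

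The first covers imputation. The general rule is "Missing data due to reasons other than death will be replaced with imputed values using the MICE method". The transplant rule follows at once: "Missing data due to lung transplant will be imputed using the MICE method even if the subject dies after lung transplant".

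The second covers deaths. It opens with "Subjects with missing assessments due to death will be ranked worse than those who remain alive" and continues with "Subjects who die will be ranked according to the time until death, with the shortest time until death as the worst rank".

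Three other places bear on the point:

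- Disease-Related Exclusions, item 5, keeps out anyone "Expected to receive a lung transplant within 6 to 12 months from randomization or on a lung transplant waiting list at randomization".
- Study Assessments states: "Subjects who undergo lung transplantation or who chose to withdraw from study procedures early will be followed for vital status until Week 52". Vital Status Assessments adds: "In the case of a subject death, the date, details, and cause of death will be requested".
- Key Secondary Efficacy Outcome Variables includes "Proportion of patients with all-cause mortality" and counts death as a progression-free survival event.

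**The concern.** Read alone, the time-to-death sentence covers everyone who dies and carries no exception for transplant. A subject who is transplanted and then dies before Week 52 would fall under it and under the transplant sentence as well. One sentence gives an imputed %FVC change, ranked with the living. The other gives a place among the deaths.

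If the text really left this open, two statisticians could get different primary p-values from the same data in a trial of about 42 subjects, and the choice could be made after the data were seen. The direction would depend on the arm. Moving such a placebo subject from an imputed rank to the death group favours pirfenidone, and moving such a pirfenidone subject works against it.

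The rule also looks odd on its merits. The date of death is collected, so a known death receives an imputed value although a death rank could be assigned. The plan gives no reason, and neither supportive analysis of the primary outcome tests the choice.

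**Working it through.** **The text**

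1. The imputation paragraph sorts by the reason a value is missing. Any reason other than death goes to multiple imputation.
2. The transplant sentence applies that principle to the one sequence where two reasons compete. Its closing clause has no function except to say that a later death does not change the handling. It is therefore an explicit exception, placed before the death rule.
3. The death paragraph defines its group in its first sentence: assessments missing because of death. Its second sentence says how that group is ordered. Read in sequence, it adds nobody whom the previous paragraph has already assigned elsewhere.
4. This fits the planned follow-up. Study Assessments puts transplanted subjects on vital-status follow-up, so transplant can coherently be taken as the event that ends the %FVC series, whatever happens later.

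Each subject therefore has one rule: missing through death, ranked at the bottom by time; missing through transplant, imputed whether or not death follows; missing for any other reason, imputed.

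**What the choice could move**

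The plan gives no transplant or death rate and no figure for this point. The inputs are 42 subjects at 2:1 (28 pirfenidone, 14 placebo), a difference of 2 and an SD of 2, all from Sample Size and Power Considerations.

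- SD of ranks 1 to 42: √(42 × 43 / 12) = 12.27.
- SE of the difference in mean ranks: 12.27 × √(1/28 + 1/14) = 4.02.

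Move one subject from imputed rank *k* to rank 1, so that the *k* − 1 subjects below each rise by one. If the arms are mixed at random, which means no treatment effect, the mean-rank difference shifts by 3(*k* − 1)/41 for a placebo subject and 3(*k* − 1)/82 for a pirfenidone subject. For *k* = 5, 10 and 21.5:

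- placebo: 12/41 = 0.29, 27/41 = 0.66, 61.5/41 = 1.50;
- pirfenidone: 12/82 = 0.15, 27/82 = 0.33, 61.5/82 = 0.75.

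At the planned effect the low ranks are mostly placebo subjects and these formulas no longer apply. Simulation used 4000 trials per cell and rank regression on treatment, rank baseline and immunosuppression, with 60% users assumed and baseline unrelated to change. The last column is the share of trials in which significance at 0.05 differs between the two rules.

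| Subject's arm | Assumed imputed rank | Shift in ranks | Shift / 4.02 | Verdict differs |
|---|---|---|---|---|
| Placebo | 5 | 0.12 | 0.03 | 1.2% |
| Placebo | 10 | 0.36 | 0.09 | 3.2% |
| Placebo | 21 | 1.10 | 0.27 | 8.9% |
| Pirfenidone | 5 | 0.32 | 0.08 | 2.5% |
| Pirfenidone | 10 | 0.63 | 0.16 | 4.9% |
| Pirfenidone | 21 | 1.11 | 0.28 | 7.7% |

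All these figures presuppose that such a subject exists. Rank 1 also presupposes that nobody died earlier. Spirometry is scheduled at Weeks 13, 26 and 39. If the imputation model uses those values, a patient declining towards transplant would be imputed low, which points to the smaller rows.

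For an unconditional figure, assume a 5% to 20% chance of one such case in the trial; the documents give no such figure. With verdict changes of 1% to 9%, the product runs from 0.05 × 0.01 = 0.05% to 0.20 × 0.09 = 1.8% of trials.

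**The case for a change.** The strongest counter-argument is that a primary analysis should not depend on the reader inferring which sentence has priority. The time-to-death sentence speaks of those who die, not of a reason for missingness, and a cross-reference to the transplant rule would remove any doubt. That much stands, but it is a matter of drafting. To reach the second result, an analyst would have to set aside a sentence that names the exact case.

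A second argument is that placing a known death among survivors defeats the purpose of ranking deaths worst. The plan also sets no sensitivity analysis for it, and one would be informative. But the plan does not say that every death must rank worst. It ranks those whose assessment is missing because of death. The alternative has its own asymmetry: transplanted survivors would stay on imputation while transplanted subjects who die took the worst ranks, so the outcome after transplant would count only when it was bad. A death caused by the transplant procedure would also be scored as a worst outcome. Experienced statisticians could defend either rule.

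A third argument is that the effect can be larger than the table shows. With imputed values drawn from the subject's own arm, one such death changed the verdict in about 5% (placebo) or 9% (pirfenidone) of simulated trials, and two in the same arm in about 10% or 20%. Those figures are sound on their terms, but two such deaths in one arm would be a remarkable event under the exclusion criteria. They show that the choice can matter if the case occurs, not that the plan leaves the choice open.

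**Conclusion.** The concern does not hold. The section gives one rule for a subject who dies after transplant, stated in advance and in terms that leave no gap. The death paragraph confines itself to a different group. A cross-reference is missing, which is a detail of drafting. The rest is disagreement with a pre-specified estimand.

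The practical reach is small. The subject must be neither listed for nor expecting a transplant at entry, and must then be transplanted and die, all within 52 weeks. With no such subject the two rules give identical results. With one, the verdict would differ in about 1% to 9% of trials under the planned effect, 28/14 allocation and assumed imputed ranks of 5 to 21. The death is not hidden: it counts in all-cause mortality and, if no earlier event occurred, as a progression-free survival event, and vital status appears in the flow diagram planned under Analysis Populations.

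The conclusion on consistency rests on the wording alone and does not depend on any of the simulated figures.

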### Study design

This is a single-center, randomized, double-blind, placebo-controlled, efficacy and safety study of pirfenidone in subjects with FHP. Approximately 42 subjects will be randomized in a 2:1 ratio to receive pirfenidone 2403 mg/d or placebo for 52 weeks. The primary efficacy endpoint is the mean change in %FVC from Baseline to Week 52, to be analyzed using a rank linear model. Subjects will receive blinded study treatment from the time of randomization until the Week 52 Visit.

Eligible subjects, males and females, aged 18–80 years (inclusive) must have a confident or high-confidence diagnosis of FHP according to pre-specified criteria without evidence of an alternative diagnosis that may contribute to their interstitial lung disease. Subjects will be required to have a FVC  $\geq$ 40% and DLCO  $\geq$ 30% at screening.

Subjects will enter the Screening Period, which may last up to 30 days. In addition of brief periods of corticosteroid use for acute FHP exacerbation, subjects will be allowed to receive any other therapy for the treatment of FHP as per pre-specified criteria.

The dose of study treatment will be titrated over 4 weeks (2 weeks at 1 capsule TID; 2 weeks at 2 capsules TID; and 48 weeks at 3 capsules TID (2403 mg/d). Pirfenidone dose modifications or interruption will be allowed for safety or tolerability reasons at any time during the study.

Subjects will have a telephone assessment at Week 1 and 3, and an in-clinic assessment at day 1, weeks 5, 13, 26, 39, and 52. Subjects will be asked to complete an adverse event (AE) and dosing compliance diary between all visits. If subjects discontinue study treatment early for any reason, they will be asked to continue with all scheduled study procedures through Week 52.

A Safety officer will review all deaths and monitor subject safety during the study.

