### **Early Discontinuation of Study Treatment**

Study treatment will be discontinued for any of the following reasons:

1. Unacceptable toxicity (this may include serious adverse events [SAEs] related to study treatment)
2. Patient request or withdrawal of consent
3. Pregnancy
4. Investigator discretion
5. Lung transplantation

Subjects who discontinue study treatment will be asked to complete all scheduled study assessments and procedures through Week 52.

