**Early Discontinuation of Study Treatment**

Subjects who discontinue study treatment before Week 52 will complete a Follow-up Visit. In addition to the procedures listed above for the Follow-up Visit, subjects who discontinue study treatment before Week 52 must return all used and unused study treatment. Subjects who discontinue study treatment will be asked to continue to complete all scheduled study assessments and procedures through Week 52.

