### **Key Secondary Efficacy Outcome Variables and Analyses**

Multiplicity adjustment will be performed across all secondary endpoints.

Progression-free survival will be compared between the pirfenidone 2403 mg/d and placebo groups using the log-rank test. A proportional hazards model will be used to estimate the hazard ratio. Descriptive analysis of progression free survival will be presented using Kaplan-Meier curves. Mortality will be analyzed using logistic regression with a treatment effect and accounting for potential over- or under-dispersion in the outcome.

The slope for annual rate of FVC decline will be analyzed using a random coefficient regression model with treatment and baseline FVC as covariates.

DLCO will be analyzed using a rank linear regression model with the rank change in %DLCO

from Baseline to Week 52 as the outcome variable and rank Baseline %DLCO and HP therapy as covariates.

Non-elective hospitalization from any cause and CT progression of fibrosis will be compared between the pirfenidone 2403 mg/d and placebo groups using logistic regression accounting for possible over- or under-dispersion in the outcome.

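### Does the plan leave open whether lung function measured after a lung transplant is analysed, and how progression-free survival treats a transplant?

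*Combined protocol and SAP*

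**What the plan says.** Three places ask for full follow-up after treatment stops. Study design: "If subjects discontinue study treatment early for any reason, they will be asked to continue with all scheduled study procedures through Week 52". The first section headed Early Discontinuation of Study Treatment has lung transplantation as item 5 of its reasons for stopping, and the sentence below the list reads "Subjects who discontinue study treatment will be asked to complete all scheduled study assessments and procedures through Week 52". The section of the same name under Study Assessments says "Subjects who discontinue study treatment will be asked to continue to complete all scheduled study assessments and procedures through Week 52". None makes an exception for transplant.

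Two places say something different about transplanted subjects. Study Assessments: "Subjects who undergo lung transplantation or who chose to withdraw from study procedures early will be followed for vital status until Week 52". Vital Status Assessments repeats this, expects the contact to be mostly remote, and lists what to obtain: "In the case of lung transplant, the date of the transplant, details of the transplant", then hospitalization dates and current vital status. Neither asks for spirometry or DLCO.

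The primary analysis section imputes: "Missing data due to lung transplant will be imputed using the MICE method even if the subject dies after lung transplant". Other subjects whose assessments are missing because of death are ranked worst.

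The secondary endpoint definition begins "Progression-free survival (PFS) defined as the time from study treatment randomization to the first occurrence of any of the following events". The list covers FVC or DLCO decline, acute exacerbation, loss of walk distance, change in background therapy, and death. Transplant is not on it. The analysis reads "Progression-free survival will be compared between the pirfenidone 2403 mg/d and placebo groups using the log-rank test", and nothing says when follow-up ends for a transplanted subject. The paragraphs on %DLCO and on FVC slope have no transplant rule.

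**The concern.** The imputation rule covers data that are missing; it does not make data missing. If a site followed the sections on stopping treatment, a Week 52 FVC from a transplanted lung would be an observed value and could be ranked as an ordinary change. That would credit a good value to the arm in which the native lung failed: a placebo transplant would then tend to hide benefit and a pirfenidone transplant to inflate it. The same could happen to %DLCO and to the FVC slope. For progression-free survival, a transplanted subject with no earlier event could be censored or carried as progression-free. A further worry is that a death after transplant is imputed over and not ranked worst, with no supportive analysis of that choice. With about 42 subjects, one patient can be visible in the result.

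**Working it through.** **Texts side by side.** The three full-follow-up sentences are general requests to anyone who stops treatment; transplant comes in only as one item of a list. The sentences in Study Assessments and Vital Status Assessments name transplanted subjects and group them with those who leave study procedures. The primary analysis section speaks of data missing because of transplant, which fits only the second reading. So the three sections that deal with the time after transplant agree: lung function is not collected, and Week 52 %FVC is imputed.

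**Inputs.** From Sample Size and Power Considerations: difference 2, SD 2, two-sided 0.05, about 42 subjects at 2:1, hence 14 and 28. The plan states at least 85% power with 13 and 25. The two-sample t-test it names gives 81.2% (normal approximation 83.3%), and 84.6% with 14 and 28. That shortfall is a separate matter and does not bear on transplant.

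**Bound by hand.** With 42 untied ranks and covariates ignored, the rank SD is √(42 × 43 / 12) = 12.27. The SE of the mean-rank difference is 12.27 × √(1/14 + 1/28) = 4.02. Moving one subject from worst to best rank adds 41 to that subject and takes 1 from everyone else:
- placebo: (41 − 13)/14 + 1 = 3.0 ranks, or 0.75 SE
- pirfenidone: (41 − 27)/28 + 1 = 1.5 ranks, or 0.37 SE

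**Simulated size.** There were 3,000 trials per scenario, with mid-study FVC correlated 0.7 with Week 52 and the worst mid-study patient of the arm transplanted. Imputation used arm and mid-study FVC. The rank regression used arm, baseline rank and an immunosuppression covariate. Without a transplant the mean-rank difference is 10.97 and power 0.81; the Monte Carlo SE is about 0.07 rank.

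| One transplant in | Imputed as planned | Value used at 25th / 50th / 75th percentile | Power, imputed | Power, value used |
|---|---|---|---|---|
| Placebo | 10.98 | 10.64 / 9.95 / 9.10 | 0.82 | 0.79 / 0.73 / 0.64 |
| Pirfenidone | 11.02 | 11.20 / 11.60 / 11.83 | 0.81 | 0.83 / 0.86 / 0.88 |

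The planned rule leaves the result unchanged within simulation error. A used value shifts it from the imputed result by at most 10.98 − 9.10 = 1.88 on placebo (0.47 SE) and 11.83 − 11.02 = 0.81 on pirfenidone (0.20 SE). With no true effect, rejection stays between 0.046 and 0.063.

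**Slope.** For visits at weeks 0, 13, 26, 39 and 52, the Week 52 weight is 26/1690 per week, and 52 × 26/1690 = 0.8. An assumed jump of 5, 10 or 20 %FVC points at Week 52 adds 4, 8 or 16 points per year to that patient's slope. That is 0.29, 0.57 or 1.14 in the placebo mean (÷14) and 0.14, 0.29 or 0.57 in the pirfenidone mean (÷28), before any shrinkage. It arises only if the value is collected and used.

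**Progression-free survival.** There were 6,000 trials per scenario, with hazard ratio 0.6, placebo event probability 0.4 to 0.8, and a sicker patient transplanted between weeks 26 and 52. In 37% to 95% of cases that patient already had an event, so no rule is needed. Counting the transplant versus carrying the patient moves the log hazard ratio by 0.01 to 0.21 SE. The largest gap is 0.563 counted, 0.626 censored and 0.634 carried, for a placebo transplant with few events. Because the event list is closed, the open choice is censored or carried; in that scenario these differ by ln(0.634/0.626) = 0.013, against an SE of 0.38 to 0.58 across scenarios.

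**The case for a change.** The best reply is that the specific rule does not cleanly override the general one, because the list of reasons for stopping treatment itself names transplantation just above the request for all assessments. The plan foresees transplants in several sections, and the entry criterion removes only candidates listed or expected at randomization, in a population selected for progression. The landmark means and the slope use unranked values, so a large jump is not bounded there as it is in the ranks. A few sentences would settle all this before anyone sees data.

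The wording conflict stands, and so does the point about unranked values: a jump of 20 points at Week 52 would matter to the slope. But these effects need three things together: a transplant, a lung-function test done despite Study Assessments and Vital Status Assessments, and an analyst who treats a donor lung as a change in the patient's own. The primary analysis section already points the analyst the other way. The random-coefficient model uses whatever visits exist, so it needs no imputation rule to run on pre-transplant visits.

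The request for a worst-rank analysis does not stand as a correction. Imputing through transplant, even with a later death, is explicit and deliberate, and the mortality endpoint still records the death. Ranking transplant worst answers another question: for two pirfenidone transplants it gives 9.61 against 10.90. That contrast is between two estimands and does not show bias in either. For progression-free survival, an event, censoring and a competing event are each defensible. The simulations have no no-transplant reference, so they show how far the rules differ, not which is right.

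**Conclusion.** No change to the plan follows. The conflicting follow-up sentences are a drafting slip; reconciling them is editorial and leaves design and analysis as they are. Setting aside lung function measured after transplant is a detail analysts would supply, since the imputation rule already treats it as missing; the same reading carries over to %DLCO and the slope. The treatment of transplant in progression-free survival is a trade-off worth at most 0.21 SE of the log hazard ratio, and analysts can record it before unblinding. The imputation rule itself is sound.

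The primary result is unaffected if there are no transplants or if the transplant-specific sections are followed. If one value between the 25th and 75th percentiles were used against them, the shift would be under 0.5 SE, though power could fall to 0.64 (placebo transplant) or rise to 0.88 (pirfenidone transplant). All these sizes rest on assumed transplant numbers, percentiles, jumps, event rates and correlations. The documents give none of these, so an expected effect cannot be computed.
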